## 1.0 Objectives / Specific Aims

- The objective of this study is to determine whether the addition of lung protective strategies to existing enhanced recovery after surgery (ERAS) protocols for colorectal surgeries and hepatobiliary surgeries will improve post-operative lung function.
- The hypothesis is that prospective subjects undergoing hepatobiliary and colorectal surgeries that have lung protective strategies added to their base ERAS protocols will have improved lung function as measured by post-operative PACU mean inspiratory capacity via incentive spirometry compared to the control group, who had the base ERAS protocols without lung protective strategies uniformly applied.

## 2.0 Background

Enhanced recovery after surgery (ERAS) protocols are evidence based care improvement processes for surgical subjects. Implementation of ERAS programs for perioperative management after surgery has resulted in major improvements in clinical outcomes and costs, making ERAS an important example of value-based care applied to surgery.

Currently, MUSC has existing ERAS protocols in place for hepatobiliary and colorectal surgeries. These uniform ERAS protocols cover fluid intake, hydration, anti-emetics, pain control, and several other considerations. Ventilator management is not standardized in ERAS protocol and is left to the discretion of the anesthetic practitioner. Numerous studies have shown improvement in perioperative surgical outcomes with the use of lung protective [ventilator] strategies. We are trying to prove that the addition of specific lung protective strategies to existing ERAS protocols can further improve subject post-operative lung function as measured by improved mean incentive spirometry inspiratory capacity readings compared to the controls.

## 3.0 Intervention to be studied (if applicable)

- A select number of researched lung protective interventions will be standardized and applied to existing and ongoing MUSC ERAS protocols for colorectal and hepatobiliary surgeries.
- The intervention arm of the study will be subjects undergoing colorectal and hepatobiliary surgeries who will have the standard ERAS protocol and lung protective strategies applied.
- The control arm of the study will be subjects going for colorectal and hepatobiliary surgeries who will have the standard ERAS protocols but will not have standardized lung protective strategies applied
- The Lung Protective Interventions to be added include:
  1. Pressure control ventilation-volume guaranteed (PCV-VG) ventilation at approximately 7cc/kg of predicted body weight (derived from combination of sex and height)
  2. Positive end-expiratory pressure (PEEP) 7cm H2O, PEEP will be titrated based on clinical needs of participants.

3. Immediately post intubation recruitment breath (30cm water for 30 seconds)
4. Every 1 hour recruitment breath (30cm water for 30 seconds)
5. 40% FIO2 initially – titrate up as necessary to maintain SPO2 >94%

## 4.0 Study Endpoints (if applicable)

- The end-point of the study will be completion of the 3rd incentive spirometry breath measurement at the 2 hour mark, whether it be in PACU or on the inpatient floor
- Study termination would include need for post-operative mechanical ventilation, need for post-op BIPAP/CPAP, admission to ICU, or inability to adhere to lung protective interventions due to subject intolerance.

## 5.0 Inclusion and Exclusion Criteria/ Study Population

### Inclusion Criteria

- All subjects going for scheduled colorectal or hepatobiliary surgery at the MUSC ART hospital who would normally be utilizing the existing ERAS protocols
- English speaking
- Able to give informed consent
- Ages 18 years and older

### Exclusion Criteria

- Emergency cases
- Pregnant subjects-confirmed by pre-operative urine pregnancy test
- Subjects with unique lung pathologies *including, but not limited to: advanced pulmonary fibrosis, lung transplantation recipients, end stage COPD, pulmonary Hypertension*
- Subjects on home O2

## 6.0 Number of Subjects

- This study will include 100 subjects in order to detect a 20% difference in the anticipated decrease in incentive spirometry inspiratory capacity breaths for the control and intervention groups.

## 7.0 Setting

- Ashley River Tower perioperative areas at MUSC.

## 8.0 Recruitment Methods

- Surgical schedules will be screened by research staff members to identify potential participants.

- An IRB approved, CITI trained, research team member that has been trained on the protocol will review the chart of potential participants to verify their eligibility.
- A study team member will approach the subject about the research study to discuss their willingness to participate in the holding room bay prior to their surgery.

## 9.0 Consent Process

- The consent process will take place in the subject's private bay in the pre-operative holding in Ashley River Tower of MUSC.
- Potential subjects will be invited to participate in the study prior to their surgery. They will be given time to ask questions and the study will be explained in detail to them. They will be given time to read the consent documents and ask any questions prior to signing consent.
- If they agree to participate in the study they will be asked to provide written consent AND sign the consent and HIPAA documents.

## 10.0 Study Design / Methods

- After obtaining informed consent, the subjects will be provided with an incentive spirometer. They will be educated in its use and will then proceed to take three separate maximum exertion inspiratory capacity breaths. All three measurements will be recorded and the subjects will then be randomized to the control or intervention group.
- They will proceed to the operating room where the existing baseline ERAS protocol for colorectal or hepatobiliary surgery will be implemented during their surgery. In addition to the existing protocols, the five lung protective strategies listed above will also be implemented throughout the course of the surgery for the intervention group.
- In the PACU, the subjects will be asked at the 30 minute, 1 hour, and 2 hour marks (time zero will be arrival to PACU) to once more take three separate maximum exertion inspiratory capacity breaths and all three measurements will be recorded.
- If the subjects are unable or unwilling to comply, this will be documented as well and re-attempted at the next scheduled study documentation milestone.
- The information that will be pulled from the subject's medical record will include age, gender, weight, height, BMI, O2 saturation, average intra-op tidal volume, and the absence or presence of supplemental O2 use.
- The data collected for the intervention subjects who will have the standardized lung protective strategies applied will then be compared to the control subjects who underwent the same surgeries and had the same colorectal and hepatobiliary protocols implemented, but without the use of standardized lung protective strategies.

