**Output:**

Noncentrality parameter $\delta$	= 2.8674419
Critical t	= 1.9934636
Df	= 72
Sample size group 1	= 37
Sample size group 2	= 37

Sample size was determined using G\*Power version 3.1.9.2 software. Using preliminary data, we estimate that we will need 37 subjects in each group (N=74) to have sufficient power (80%) at alpha=0.05 to test the hypothesis of a difference in mean change in IS for the two groups. To account for attrition due to withdrawals, we intend to enroll 50 patients per group. In the event that no withdrawals occur, enrolling 100 subjects (50 in each group) will give 91% power to distinguish between the two groups.

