**Input:**

Tail(s)	= Two
Effect size d	= 0.6666667

$\alpha$ err prob	= 0.05
Sample size group 1	= 50
Sample size group 2	= 50
Output: Noncentrality parameter $\delta$	= 3.3333335
Critical t	= 1.9844675
Df	= 98
Power (1- $\beta$ err prob)	= 0.9099634

Baseline clinical and demographic factors for each group will be collected. Categorical data will be compared across the two groups with Chi-square tests of homogeneity and continuous data will be compared with t-tests for means. Covariates determined to be associated with IS measurement will be assessed for inclusion in a multivariate linear model.

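### Two kinds of operation are pooled without stated stratification, and surgery type is neither a named data item nor a pre-specified term in the primary analysis

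*Combined protocol and SAP*

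**What the plan says.** Section 5.0 admits "All subjects going for scheduled colorectal or hepatobiliary surgery at the MUSC ART hospital", subject to the other criteria. Section 10.0 says that in the operating room "the existing baseline ERAS protocol for colorectal or hepatobiliary surgery will be implemented during their surgery", so the background care depends on which operation the subject has.

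The only statement on allocation is in Section 10.0: "the subjects will then be randomized to the control or intervention group". The documents do not describe stratification, blocking or how the sequence is generated. Section 11.0 plans an allocation ratio of 1 and says "we intend to enroll 50 patients per group".

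The items to be taken from the medical record "will include age, gender, weight, height, BMI, O2 saturation, average intra-op tidal volume, and the absence or presence of supplemental O2 use" (Section 10.0). Surgery type is not among them.

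The primary analysis in Section 11.0 is a two-sided test of mean change in incentive spirometry (IS), with no term for operation. At the end of that section the plan adds "Baseline clinical and demographic factors for each group will be collected" and "Covariates determined to be associated with IS measurement will be assessed for inclusion in a multivariate linear model". It names no covariates.

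**The concern.** Colorectal and hepatobiliary operations may reduce inspiratory capacity by different amounts. If so, an arm that by chance receives more of the harder-hit operation shows a larger mean loss for reasons unrelated to ventilation, and the stated primary test has no means of separating the two. Over repeated trials, the same variation between operations sits in the error term and lowers power.

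Section 10.0 describes the comparison as one with controls who had the same surgeries, yet nothing in the design secures a similar mix of operations in the two arms. The last sentence of Section 11.0 would bring surgery type into a model only if it were found to be associated with IS in the trial's own data. That makes the adjustment a choice taken after the data are seen, and outside the stated primary test.

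**Working it through.** **Inputs from the documents (Section 11.0).** Mean change about 1000 mL in controls and 800 mL in the intervention group, a difference of 200 mL; shared SD 350 mL; two-sided alpha 0.05; 50 per arm.

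**Inputs assumed, because the documents do not give them.** Hepatobiliary share p of 30% to 50%. Gap D in mean change between the two operations of 100, 200 or 300 mL. The 350 mL is taken as the total SD, including variation between operations.

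**1. The plan's own figures.** With d = 0.6667, the two-sample t-test needs 36.3, rounded up to 37 per group, and gives 91.0% power at 50 per group. Both stated figures reproduce. The text's own inputs, however, give d = 200/350 = 0.571, and power at 50 per group is then 80.8%. A d of 0.667 would need an SD of 200/0.667 = 300 mL. That mismatch is a separate matter; 80.8% is used below as the reference because it follows from the stated difference and SD.

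**2. How large chance imbalance can be.** With arms fixed at 50 each, the number of hepatobiliary cases in one arm is hypergeometric. The SD of the between-arm difference in share is (2/50) × √[50 × p(1−p) × 50/99].
- p = 0.3: (2/50) × √5.303 = 9.2 points.
- p = 0.5: (2/50) × √6.313 = 10.0 points.

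The probability of a difference of at least 10 points is 0.28 (p = 0.3) or 0.32 (p = 0.5), and of at least 20 points 0.05 or 0.07. If allocation were simple randomisation, so that arm sizes also vary, simulation gives 0.29 to 0.37 for at least 10 points and 0.10 to 0.13 for at least 15 points.

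**3. What an imbalance does to the estimate.** Shift = imbalance × D. With a 15-point imbalance and D = 200 mL, the shift is 0.15 × 200 = 30 mL, which is 15% of the planned 200 mL. The standard error at 50 per arm is 350 × √(2/50) = 70 mL, so the shift is 30/70 = 0.43 standard errors.

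**4. What accounting for surgery type gains.** Within-operation SD = √[350² − p(1−p)D²]; power is then from the noncentral t at 50 per arm.

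| D (mL) | SD, p = 0.3 | SD, p = 0.5 | Power, p = 0.3 | Power, p = 0.5 |
|---|---|---|---|---|
| none (reference) | 350 | 350 | 80.8% | 80.8% |
| 100 | 347 | 346 | 81.4% | 81.6% |
| 200 | 338 | 335 | 83.4% | 83.9% |
| 300 | 322 | 316 | 86.8% | 87.9% |

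The one degree of freedom spent on the extra term is ignored here; it is negligible against 98. With a total SD of 300 mL instead, the reference is 91.0% and the three gaps give 91.6-91.7%, 93.4-93.8% and 96.0-96.8%.

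**5. Steps 3 and 4 describe one cost, not two.** With p = 0.5 and D = 200 mL, imbalance adds an SD of 0.1005 × 200 = 20 mL to the estimate. Removing it from the 70 mL standard error leaves √(70² − 20²) = 67 mL, which matches 335 × √(2/50) = 67 mL. The shift in a single trial and the precision lost on average should not be added together.

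**The case against.** The strongest reply is that the plan is already valid. Randomisation without strata is unbiased on average, the t-test keeps its type I error, and chance imbalance in surgery mix is already reflected in the unadjusted standard error. That stands. It is also fair that the benefit depends on a gap between operations that the documents do not give: at 100 mL the gain is under one percentage point of power.

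Three stronger readings are tempting, and the documents do not support them.

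- *That surgery type cannot be adjusted for as the plan is written.* The Section 10.0 list covers items from the medical record and is worded as what the data will include, not as a closed list. Section 11.0 provides for baseline clinical factors and a multivariable model, which could contain surgery type. The operation is also known to the team, since Section 8.0 has staff screen surgical schedules. What can be said is that surgery type is not named and its adjustment is not pre-specified.
- *That randomisation is unblocked.* The documents are silent on method. They plan equal allocation and 50 per group, and any figure based on simple randomisation is an assumption.
- *That unequal arm sizes would damage power.* Under simple randomisation of 100, a split of 45/55 or worse has probability 0.37, but a 45/55 split lowers power only from 80.8% to 80.4%. Even 40/60 gives 79.2%.

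What the reply does not answer is why a known factor, available before allocation, should be left to selection on the trial data when naming it in advance costs almost nothing.

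**Conclusion.** The point holds as a cheap improvement, not as an error in the plan. No stratification by operation is stated, surgery type is not a named data item, and the primary test has no term for it. The gain in power at 50 per arm is about 1, 3 or 6-7 percentage points for a gap between operations of 100, 200 or 300 mL. This rests on the assumed 30-50% hepatobiliary share, on 350 mL being the total SD, and on no withdrawals. If the two operations have the same mean change, there is no gain.

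A modest gain is still worth taking here. On the stated 200 mL and 350 mL, the trial has about 81% power at full enrolment and about 68% if withdrawals leave 37 per group, so there is little to spare.

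**What to change.** In Section 10.0, add scheduled surgery type (colorectal or hepatobiliary) to the data items, and state that subjects are randomised 1:1 in permuted blocks of varying size, stratified by scheduled surgery type. In Section 11.0, state that the primary comparison of change in IS comes from a linear model with treatment and surgery type as fixed terms, and that surgery type is included whatever its observed association with IS.

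If only part of this is adopted, recording surgery type and pre-specifying the model term matter most; stratified blocks complement them.

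The cost is one field to enter at randomisation, already known from the surgical schedule, two allocation lists instead of one, and one degree of freedom in the model. The REDCap database already planned in Section 11.0 could hold the field. No extra subjects or visits and no change to clinical care are needed.

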## 11.0 Data Management

- The primary outcome of interest is the inspiratory capacity obtained in the PACU via the incentive spirometer.
- The secondary outcomes that will be observed are the numerical value for SPO2, SPO2 trend, and use or lack thereof of supplemental O2 in PACU in 15 minute intervals or up to two hours after arrival there.

- Our primary hypothesis is that subjects that will have lung protective strategies employed on them will have 20% superior mean inspiratory capacity breaths via incentive spirometry compared to the non-intervention controls.
- Only IRB approved study team members will have access to data. Each study subject will be given a study ID number that will be used to identify them throughout the study. All study staff will have their CITI certification and receive protocol training. All data will be kept on a password protected MUSC server and in a redcap database. All paper documents will be kept in a locked office, in a locked cabinet that only IRB study team members have access to.
- Our primary hypothesis is that use of lung protection protocol will result in smaller change in lung function, measured by Incentive Spirometry (IS).

$H_0$ : change in ISI ≠ change in ISC

$H_A$ : change in ISI < change in ISC

The primary analysis will be a two-sided test of mean change in IS after surgery compared to pre-surgery IS.

Based on data from a study of 19 people undergoing lobectomy {Bastin, 1997 #14268}, we assume that the IS before surgery is 2642 mL (se=140; std=610). If the control group IS decreases by 40%, the mean change in the control group will be ~1000 mL (std dev=308). Assuming the intervention group IS decreases by 30%, the mean change in the intervention group will be ~800 mL. Assume shared std dev=350.

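### The primary outcome depends on effort, but the protocol does not keep the subject or the person taking the post-operative readings unaware of the arm

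*Combined protocol and SAP*

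**What the plan says.** Section 11.0 names the outcome: "The primary outcome of interest is the inspiratory capacity obtained in the PACU via the incentive spirometer". The primary analysis there is a two-sided comparison of mean change from the pre-operative value.

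Section 10.0 gives the order of events. Before surgery, subjects are taught the device: "They will be educated in its use and will then proceed to take three separate maximum exertion inspiratory capacity breaths". Then: "All three measurements will be recorded and the subjects will then be randomized to the control or intervention group". In the operating room, "the five lung protective strategies listed above will also be implemented throughout the course of the surgery for the intervention group". At 30 minutes, 1 hour and 2 hours after arrival in PACU, subjects are asked "to once more take three separate maximum exertion inspiratory capacity breaths and all three measurements will be recorded". Section 4.0 allows the 2-hour reading to be taken on the inpatient floor.

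The protocol recognises that the reading needs the subject's cooperation: "If the subjects are unable or unwilling to comply, this will be documented as well and re-attempted at the next scheduled study documentation milestone".

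No section mentions blinding or masking of the subject, the reader or the analyst. None says who takes the post-operative readings, whether that person knows the arm or was in the operating room, or what instructions are used. Two provisions in Section 11.0 come closest: "Only IRB approved study team members will have access to data" and "Each study subject will be given a study ID number that will be used to identify them throughout the study". Both protect confidentiality. Neither is said to conceal the arm.

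**The concern.** A maximal inspiratory effort is partly voluntary. In a patient just out of surgery, the volume reached can vary with motivation and with the encouragement given at the bedside. If the subject or the reader knows the arm, and both know what the study hopes to show, effort or encouragement can differ between arms in the hypothesised direction.

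Because the baseline breaths precede randomisation, they cannot carry an arm-related bias. That protects the baseline, but it also means that a bias in the post-operative readings has nothing to cancel against: all of it enters the change score, and so the primary between-arm difference. The covariate model in Section 11.0 cannot remove it, because the bias travels with the arm itself. A larger sample only estimates the biased difference more precisely. At stake is whether a positive result could be attributed to the ventilation strategy.

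**Working it through.** **Inputs from Section 11.0.** Baseline 2642 mL; control fall 40%, taken as about 1000 mL; intervention fall 30%, taken as about 800 mL; planned difference 200 mL; shared SD of change 350 mL; effect size entered in G*Power d = 0.6667; two-sided alpha 0.05; 37 per group required, 50 per group to be enrolled. With a 200 mL difference, d = 0.6667 implies an SD of 200/0.6667 = 300 mL rather than 350 mL, so both values are carried through.

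**Assumed input.** A constant bias *b* in mL, favouring the intervention arm in the mean change. The documents give no value.

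**Step 1: reproduce the plan's figures.** For a two-sample t-test, the noncentrality is d × √(n/2) with 2n − 2 degrees of freedom.
- n = 37: 0.6667 × √18.5 = 2.867, critical t 1.9935, power 0.808. The plan's 37 per group reproduces.
- n = 50: 0.6667 × √25 = 3.333, critical t 1.9845, power 0.910. The plan's 91% reproduces.

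**Step 2: smallest observed difference that is significant, 50 per arm.** The standard error is SD × √(2/50) = 0.2 × SD.
- SD 350: 0.2 × 350 = 70 mL; 1.9845 × 70 ≈ 139 mL.
- SD 300: 0.2 × 300 = 60 mL; 1.9845 × 60 ≈ 119 mL.

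**Step 3: false-positive rate under an assumed bias.** Set the true effect to zero and take the noncentrality as *b* divided by the standard error. The rejection probability (both tails, noncentral t, 98 degrees of freedom) is:

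| Assumed bias | Noncentrality, SD 350 | Rejection, SD 350 | Noncentrality, SD 300 | Rejection, SD 300 |
|---|---|---|---|---|
| 0 mL | 0 | 5.0% | 0 | 5.0% |
| 50 mL | 50/70 = 0.71 | 10.9% | 50/60 = 0.83 | 13.1% |
| 100 mL | 100/70 = 1.43 | 29.3% | 100/60 = 1.67 | 37.9% |
| 150 mL | 150/70 = 2.14 | 56.4% | 150/60 = 2.50 | 69.7% |
| 200 mL | 200/70 = 2.86 | 80.8% | 200/60 = 3.33 | 91.0% |

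**Step 4: effect of sample size.** With 37 per arm and SD 350, the 50 and 100 mL rows become 9.3% and 22.8%. Moving from 37 to 50 per arm raises the error rate, so enrolling more subjects is no remedy.

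**Step 5: scale.** A 40% fall leaves a control value of 0.60 × 2642 = 1585 mL. A bias of 50 mL is 3.2% of that and 100 mL is 6.3%. (With the plan's rounded fall, 2642 − 1000 = 1642 mL, they are 3.0% and 6.1%.)

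**Step 6: is masking the subject feasible?** Section 3.0 lists five interventions, all of them ventilator settings or recruitment manoeuvres, and Section 10.0 places them in the operation. An anaesthetised subject does not perceive them and would learn the arm only by being told.

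**The case against.** The strongest reply is that the gap is one of silence. A reader might infer that the trial is open-label, that subjects are told their arm, or that staff coach the readings. The documents support none of these. They never call the trial open-label. Being randomised while awake is not the same as being informed. Section 10.0 says that subjects are taught the device before randomisation and asked for breaths afterwards; it describes no coaching in PACU. The consent form is not in the text available, so masking wording there cannot be excluded. All of this stands, and it limits the point to an absent safeguard.

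Some protection already exists. Three breaths at each of three set times are specified, all values are recorded, staff receive protocol training, and the baseline is taken before allocation. The number of attempts therefore needs no change, and what is missing is the wording of the instruction.

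The bias sizes are assumed. The 50 and 100 mL cases are a quarter and a half of the planned difference, and with a 100 mL bias at SD 350 about 71% of null trials would still be non-significant. That is fair, and the rates are conditional illustrations.

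What does not follow is that silence is harmless. Staff who follow the protocol exactly may know the arm and may tell the subject, and nothing in it asks them to do otherwise.

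**Conclusion.** The concern holds in a limited form. The primary outcome is effort-dependent and measured after randomisation, and nothing in the protocol keeps the subject or the reader unaware of the arm. The exposure is confined to the post-operative readings, where any arm-related bias enters the change score in full.

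The size is unknown. If a bias of 50 mL existed with no true effect and 50 per arm, the nominal 5% error would be about 11% (SD 350) or 13% (SD 300). At 100 mL it would be about 29% or 38%. These figures assume a constant bias towards the intervention arm, the plan's t-test and no attrition. They show how sensitive the test is. A reader might infer from them that bias will occur, or that it would match the planned 200 mL effect; the documents support neither inference.

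The change should be made, because two of its three parts need no extra staff and the weakness cannot be repaired at analysis.

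**What to change.** Amend Section 10.0 as follows.

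1. Subjects are not told their arm until after the 2-hour reading. Align the consent wording with this.
2. Every post-operative reading, including a 2-hour reading on the inpatient floor, uses one fixed instruction script. Keep the three breaths per time point already specified.
3. Where existing staffing allows, the reader is someone who did not randomise the subject or work in the operating room, and who is not told the arm. Record at each reading whether the reader knew the arm, and use that record in a sensitivity analysis of the primary comparison.

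Items 1 and 2 are worth having even where item 3 cannot be met. The anaesthetic practitioner cannot be masked and need not be.

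Cost: protocol text, a short script, one extra data field, a minor consent or IRB wording change, and some rostering of existing staff. No extra assessor or procedure is needed, and the ventilation strategy is untouched.
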